4.2. Stopping Rules

The Sponsor or the clinical investigator can suggest suspension of the clinical trial at any time if they are in receipt of information that leads them to believe that continuing the study jeopardizes the health and welfare of the clinical trial participants. Suspension of the study will be considered if two or more consecutive severe ocular injuries or 2 or more subjects requiring explant due to visual intolerance of the device occur at any one clinical site that are related to the surgical procedure and/or IOPCL AMD-MAG device. A severe ocular injury results in a permanent impairment of a vision or permanent damage to an eye.

Examples:

- Uveitis-Glaucoma-Hyphema (UGH) Syndrome. Intraocular chafing from the IOPL/PCIOL implant leading to a spectrum of iris transillumination defects and pigmentary dispersion to microhyphemas with elevated intraocular pressure.
- Posterior capsule rupture with IOPL/PCIOL dislocation resulting in a posterior vitrectomy during the surgical procedure.

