2. STUDY DESIGN

This will be a 12-month study, in which a maximum of 10 pseudophakic subjects from three clinical sites with a diagnosis of age-related macular degeneration will be enrolled. In order to minimize bias, investigators recruited for this study will not have prior surgical experience with the IOPCL.

This study is being conducted in accordance with 21 CFR Parts 50, 54, 56 and 812.42 (U.S.C 282(j)). ISO 14155 Clinical investigation of Medical Devices for Human Subjects, ISO 11979-7, and the ethical principles laid down in the Declaration of Helsinki.

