6.1. Outcome Simulation Testing

After informed consent has been obtained the subject will be required to participate in a "Outcome Simulation test." First, the subject's manifest refraction will be placed in a trial frame. Next, using the add power of commonly-used spectacles, a +3.0D lens will be placed into the trial frame and near visual acuity will be tested using the Sloan Near Vision Chart at 30 centimeters (11.5 inches) and at the subject's preferred reading distance (i.e., the distance at which the subject can most clearly see the chart or reading material). Then, the +3.0D lens will be exchanged for a +7.0D lens and near visual acuity will be assessed using the Sloan chart at 14 centimeters (5.5 inches) and the

subject's preferred reading distance. This will closely simulate the expected outcome after surgery and determine if he/she can tolerate the high magnification. Subjects who demonstrate at least 10 letters of near visual acuity improvement with the +7.0D lens, compared to near visual acuity achieved with the +3.0D lens, will have the option to continue with the remaining pre-operative testing or to withdraw from the study. Subjects who fail to achieve at least 10 letters of near visual acuity improvement with the simulation testing or who are not completely tolerant of their vision during the simulation testing will be exited from the study.

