12.1.7. Removal of the IOPCL

The IOPCL is only to be removed for specific causes such as, but not limited to, subject intolerance, damage to the IOPCL and/or base PCIOL, and adverse events being caused by the presence of the IOPCL (e.g., pupillary block or reduced vision).

Removal of the IOPCL will be recorded. **Prior to recording, please ensure that the video equipment is in full working order**. Video recordings will be shared with the Sponsor and FDA.

REMOVAL INSTRUCTIONS:

Re-open the initial incisions or create new access into the anterior chamber if they have healed. With ProVisc in the anterior chamber use a Sinskey hook or similar instrument to disengage the three IOPCL haptics from their respective channels. Place a small amount of ProVisc between the IOPCL and existing PCIOL to separate them apart. Using micro-forceps thru the 2.0 mm wide incision, grasp the anterior and posterior surface of the IOPCL and remove it through the incision. The IOPCL is flexible and will fold and achieve a "taco" form for removal in one piece. After explantation of the complete IOPCL, assess the lens surface of the existing PCIOL for any damage. If any damage is noticed on the existing PCIOL particularly on its lens surface, please record this on the IOPCL removal Case Report Form. Remove the remaining ProVisc, irrigate and close the wound per your normal PCIOL procedures.

Please return the removed IOPCL to the Sponsor for damage assessment.

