17. ADVERSE EXPERIENCE AND COMPLICATION REPORTING

Throughout the course of the proposed study, all efforts will be made to remain alert to possible adverse experiences or untoward findings. If adverse experiences occur, the first concern will be the safety and welfare of the subject and appropriate medical intervention will be made. Any adverse experiences observed by the investigator or reported by the subjects, whether or not ascribed to the investigational procedure or device, will be recorded on the subject's adverse event case report form. A new adverse event case report form is used for each adverse event or adverse event-related visit.

Any serious adverse events (SAEs) and unanticipated adverse device events (UADE), whether ascribed to the investigational device or not, will be communicated as soon as possible to OnPoint Vision Inc. and to the IRB. These reports must be confirmed in writing within 5 working days of learning of the occurrence. Any subjects who are terminated from the study due to adverse experiences will be followed and documented until their medical outcome is determined, and a written report provided to OnPoint Vision Inc. by the investigator.

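### The numeric suspension trigger in Protocol 4.2 counts within a site, so two or three related events of one type at different sites do not meet it

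*Protocol*

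**What the plan says.** Protocol Section 2 plans for "a maximum of 10 pseudophakic subjects from three clinical sites". Neither document states how the subjects divide among the sites.

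Protocol 4.2 has two routes to suspension. The first is discretionary and has no number: the sponsor or an investigator "can suggest suspension of the clinical trial at any time" on welfare grounds. The second is numeric: "Suspension of the study will be considered if two or more consecutive severe ocular injuries" occur, or at least two explants for visual intolerance. The site phrase closes that list: "consecutive severe ocular injuries or 2 or more subjects requiring explant due to visual intolerance of the device occur at any one clinical site". Only events related to the procedure or device count.

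Other routes by which events become known:

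- Protocol 17: serious events, "whether ascribed to the investigational device or not, will be communicated as soon as possible" to the sponsor and the IRB.
- Protocol 12.1.7: "Please return the removed IOPCL to the Sponsor for damage assessment".
- SAP 6.8: one interim analysis after every enrolled subject has attended or missed the 4–6 month visit or has left the study, plus interim safety summaries for annual reports.

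None of these states a count at which suspension must be considered.

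**The concern.** In a study of 10 eyes, two or three related harms are a realistic form for a safety signal to take. The numeric rule is the only place where the protocol turns a count into a duty to consider suspension, and on the explant limb that count restarts at each site. One intolerance explant per site is up to 30% of the study (3 of 10), yet the rule is silent.

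The injury limb is less clear. The likelier reading applies the site phrase to it as well. A second reading attaches that phrase to explants alone and runs *consecutive* through the whole trial. On either reading, an uneventful eye between two injured ones breaks the sequence.

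At stake is whether scattered related events prompt a required review, or one that depends on somebody choosing to ask for it.

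**Working it through.** **Inputs.** From the documents: at most 10 subjects, three sites, threshold two. Assumed: every split with at least one subject per site (eight splits, 8/1/1 to 4/3/3), event risks of 5% to 30%, equal risk and independence unless stated. The plan gives no operating figure for the rule, so there is none to reproduce.

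**Step 1: logic, with no assumption about risk.** Three events, one per site, never put two at one site. A fourth must share a site with another. So up to three explants can leave the trigger unmet.

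**Step 2: share of patterns that miss a same-site count.** For site sizes a, b, c:

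- Two events miss in ab + ac + bc of C(10,2) = 45 patterns.
  - 4/3/3: 12 + 12 + 9 = 33, so 73%.
  - 8/1/1: 8 + 8 + 1 = 17, so 38%.
- Three events miss in abc of C(10,3) = 120 patterns.
  - 4/3/3: 36, so 30%.
  - 8/1/1: 8, so 7%.

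The other six splits lie between these.

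**Step 3: injuries, reading *consecutive* as adjacent subjects.**

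- Adjacent within a site: there are (a−1) + (b−1) + (c−1) = 7 adjacent pairs for any split. Two injuries miss in 45 − 7 = 38 of 45 (84%). By enumeration, three miss in 68–70 of 120 (57–58%).
- Adjacent in trial-wide order: there are 9 adjacent pairs. Two miss in 36 of 45 (80%). Three miss in C(8,3) = 56 of 120 (47%).

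**Step 4: probability that the trigger is reached at true risk p.**

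- Same-site: 1 − ∏[(1−p)^n + np(1−p)^(n−1)] over sites of size n. At p = 0.10 and 4/3/3 this is 1 − 0.9477 × 0.972² = 0.105.
- Pooled two: 1 − (1−p)^10 − 10p(1−p)^9. At p = 0.10 this is 1 − 0.3487 − 0.3874 = 0.264.

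| Rule | 5% | 10% | 20% | 30% |
|---|---|---|---|---|
| Same-site two, 4/3/3 | 2.8% | 10.5% | 34% | 60% |
| Same-site two, 8/1/1 | 5.7% | 18.7% | 50% | 75% |
| Adjacent at a site | 1.7% | 6.3–6.5% | 22–23% | 42–44% |
| Adjacent, trial-wide | – | 8% | 27% | 50% |
| Pooled two | 8.6% | 26% | 62% | 85% |

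**Step 5: clustering by site.** If events cluster by surgeon, a site count performs better. With a beta-binomial model, split 4/3/3 and an assumed intraclass correlation of 0.3, two events miss in 30–47% and three in 3–9% (risks 10–30%). At 20% risk the site count is reached in 46% of trials and a pooled two in 56%. The gap narrows but remains.

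**The case against.** **Pooled oversight already exists.** A reader might infer that nobody has to look across sites. The documents do not support that. SAP 6.8 commits to an interim analysis and annual safety summaries, and SAP 7.5.3 and 7.5.6 tabulate interventions and adverse events over all eyes. The monitoring plan and Appendix 5 are not available here and may add duties. What stands is narrower: no threshold is attached to any of these looks in the protocol or SAP, and the interim analysis may come after the last implant.

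**The change is small.** Suspension can be suggested at any time, and the numeric rule itself only requires that it be considered. In 10 eyes an attentive sponsor may well notice scattered events. That is fair, and it limits the benefit. But the protocol chose to write a duty alongside the discretion, and the point is where that duty does not reach.

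**A site rule has a reason.** Protocol Section 2 says that "investigators recruited for this study will not have prior surgical experience with the IOPCL", so surgical injuries may cluster by surgeon. This stands, and is why the site rule should stay. A reader might go further and say that a site rule makes no sense for intolerance, because Protocol 6.1 uses a preoperative test to "closely simulate the expected outcome after surgery and determine if he/she can tolerate the high magnification". That section does not define explant for visual intolerance. A misaligned optic, listed as an adverse event in Protocol 16.3, could contribute to intolerance and could depend on the surgeon.

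**The headline case is uncommon.** Exactly three events, one per site, has probability 36p³(1−p)⁷ at 4/3/3: 1.7%, 6.0% and 8.0% at risks of 10%, 20% and 30%. This stands. The percentages in Step 2 are conditional on the events having happened. Nor do the documents name an unacceptable event rate, so the trigger probabilities describe the rule and do not by themselves prove its threshold wrong.

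**A pause may spare no one.** Intolerance may emerge after all eyes are implanted. A reader might infer a fixed number of implantations avoided, but that would need every event to be known before the next surgery, and the documents give no event or accrual timing.

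**Conclusion.** The point holds as a gap in Section 4.2 that is worth fixing. Site-only counting is certain for explants and probable for injuries, where the undefined *consecutive* narrows the rule further. That three explants, one per site, leave the trigger unmet follows from the wording alone. The size (two events missing in 38–73% of patterns, three in 7–30%) rests on independence and equal risk across the possible splits, and it shrinks if events cluster by site. The conclusion is not that safety goes unreviewed. It is that no stated count obliges anyone to consider suspension when related events of one type are spread across sites.

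**What to change.** Keep the site rule, delete *consecutive* from it, and add to Protocol 4.2: *Suspension will also be considered when two severe ocular injuries, or two explants for visual intolerance, related to the procedure and/or device have occurred over all implanted subjects at all sites.*

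With a pooled two, the site rule adds no trigger of its own but still directs attention to a surgeon or site. If the sponsor and medical monitor prefer a pooled three, the site rule is essential. A pooled three alone is reached in 7%, 32% and 62% of trials at risks of 10%, 20% and 30%, which at the first two is below the same-site count at 4/3/3 (10.5% and 34%). Pooled three plus the site rule without *consecutive* gives 12%, 40% and 68% at 4/3/3. Each event type is counted separately, so one injury plus one explant would still not meet the rule. The sponsor should decide whether that is intended.

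The cost is a one-sentence amendment with no new data flow, and more frequent reviews. Against a same-site count, the trigger is reached in 8.6% rather than 2.8–5.7% of trials at 5% risk, and 26% rather than 10.5–18.7% at 10%. For injuries, if *consecutive* now means adjacent at a site, the rise is larger: from 1.7% to 8.6%, and from 6.3–6.5% to 26%. Each is a review, not an automatic stop.

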4.3. Primary Effectiveness Endpoint

Proportion of eyes ($\geq 75\%$) able to achieve improvement of 10 letters or more of uncorrected near visual acuity (at 14 cm) at 12 months from baseline.

4.4 Secondary Effectiveness Endpoints

- Proportion of eyes (≥ 50%) able to achieve improvement of 20 letters or more of uncorrected near visual acuity (at 14 cm) at 12 months from baseline.
- Proportion of eyes (≥ 75%) able to achieve improvement of 10 letters or more when comparing uncorrected near visual acuity (UCNVA) (at 14 cm) at 12 months from baseline BCNVA (at 30 cm, wearing the appropriate preoperative distance refractive correction in addition to +3.0D add).
- Proportion of eyes (≥ 50%) able to achieve improvement of 20 letters or more when comparing uncorrected near visual acuity (UCNVA) (at 14 cm) at 12 months from baseline BCNVA (at 30 cm, wearing the appropriate preoperative distance refractive correction in addition to +3.0D add).
- Proportion of eyes (≥ 75%) able to achieve improvement of 10 letters or more when comparing best corrected near visual acuity (BCNVA) (at 14 cm) at 12 months from baseline BCNVA (at 30 cm, wearing the appropriate preoperative distance refractive correction in addition to +3.0D add).
- Proportion of eyes (≥ 50%) able to achieve improvement of 20 letters or more when comparing best corrected near visual acuity (BCNVA) (at 14 cm) at 12 months from baseline BCNVA (at 30 cm, wearing the appropriate preoperative distance refractive correction in addition to +3.0D add).

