5.1. Inclusion Criteria

- 1. Subjects aged 55 years or older.
- 2. Subjects who have already had cataract surgery with an Alcon SN60WF, SA60AT or SA60WF monofocal intraocular lens with a lens power between 17.0 diopters and 24.0 diopters clearly evidenced by photographic documentation by one of the following:
 - patient medical record
 - clinic chart with labeling attached
 - surgical record with labeling attached, or
 - patient identification card with make, model and serial number.
- 3. Subjects who have already had cataract surgery at least 6 months from the planned date of the IOPCL surgery.
- 4. Subjects with non-neovascular dry AMD or stable wet AMD meeting the following criteria:
 - No macular fluid retention in the past 12 months
 - No treatment within the past 12 months
 - No change in Amsler Grid test within the past 12 months
 - No subretinal fluid or macular hemorrhage confirmed by optical coherence tomography (OCT) imaging.
 - No fundoscopic changes within the past 12 months (i.e., changes in retinal pigment epithelium).
- 5. Subjects with best corrected distance visual acuity from 20/80 to 20/800.
- 6. Subjects with a preoperative manifest refraction spherical equivalent (MRSE) of +1.0D to -1.0D.
- 7. Subjects with ≤1.0D of corneal cylinder determined by keratometry readings.
- 8. Subjects who are unsatisfied with their current near vision correction provided by either spectacles or external magnifier.
- 9. Subjects who have experienced and failed one or more high-magnification refractive correction alternatives to the IOPCL AMD-MAG.

- 10. Subjects who demonstrate at least 10 letters of near visual acuity improvement with the simulation/tolerance test (using manifest refraction with +7.0D add) compared to conventional near vision testing (using manifest refraction with +3.0D add).
- 11. Subjects with a minimum endothelial cell count of 1800 cells/mm².
- 12. Subjects willing to abstain from pursuing any other surgical vision-correcting procedures for the duration of the study.
- 13. Subjects who are willing and able to complete all required postoperative visits.
- 14. Subjects who are able to comprehend and sign a statement of informed consent.

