- IOPCL Location (following dilation): 1-2 days, 7-14 days, 30-60 days, 120-180 days, 330-420 days, Interim
- Manifest Refraction: Preoperative, 7-14 days, 30-60 days, 120-180 days, 330-420 days, Interim
 - Post-removal, 7-14 days, 30-60 days, 120-180 days, 330-420 days, Interim
- Add Power: Pre-Operative, 7-14 days, 30-60 days, 120-180 days, 330-420 days, Interim.
 - Post-removal, 7-14 days, 30-60 days, 120-180 days, 330-420 days, Interim
- BCDVA: Best Corrected Distance Visual Acuity (at 6m) Preoperative, 7-14 days, 30-60 days, 120-18 days, 330-420 days, Interim
 - Post-removal, 7-14 days, 30-60 days, 120-180 days, 330-420 days, Interim
- BCNVA: Best Corrected Near Visual Acuity (at 30 cm (preoperatively); 14 cm (postoperatively) and preferred reading distance (preoperatively and postoperatively)) Pre-Operative, 7-14 days, 30-60 days, 120-180 days, 330-420 days, Interim.
 - Post-removal, 7-14 days, 30-60 days, 120-180 days, 330-420 days, Interim

- UCDVA: Uncorrected Distance Visual Acuity (at 6m)— Preoperative, 7-14 days, 30-60 days, 120-180 days, 330-420 days.
 - Post-removal, 7-14 days, 30-60 days, 120-180 days, 330-420 days. Interim
- UCNVA: Uncorrected Near Visual Acuity (at 14 cm and preferred reading distance) –
 Preoperative, 7-14 days, 30-60 days, 120-180 days, 330-420 days
 - Post-removal, 7-14 days, 30-60 days, 120-180 days, 330-420 days, Interim
- Central Visual Field (Amsler Grid): Preoperative
- Reading Speed (Smith-Kettlewell testing at 40 cm): Preoperative, 7-14 days, 30-60 days, 120-180 days, 330-420 days
 - Post-removal, 7-14 days, 30-60 days, 120-180 days, 330-420 days, Interim
- Contrast Sensitivity (Mesopic): Preoperative, 7-14 days, 30-60 days, 120-180 days, 330-420 days
 - Post-removal, 7-14 days, 30-60 days, 120-180 days, 330-420 days, Interim
- Slit Lamp Examination: Preoperative, 1-2 days, 7-14 days, 30-60 days, 120-180 days, 330-420 days, Interim.
 - Post-removal, 1-2 days, 7-14 days, 30-60 days, 120-180 days, 330-420 days, Interim
- Gonioscopy: 7-14 days, 30-60 days, 120-180 days, 330-420 days, Interim
 - Post-removal, 7-14 days, 30-60 days, 120-180 days, 330-420 days, Interim
- Intraocular Pressure: Preoperative, 1-2 days, 7-14 days, 30-60 days, 120-180 days, 330-420 days, Interim
 - Post-removal, 1-2 days, 7-14 days, 30-60 days, 120-180 days, 330-420 days, Interim
- Dilated Fundoscopy: Preoperative, 7-14 days, 30-60 days, 120-180 days, 330-420 days, Interim

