## 3.1.2 Secondary Effectiveness Endpoints

The secondary effectiveness endpoints identified for this Early Feasibility Study for IOPCL AMD-MAG are:

- Proportion of eyes (≥ 50%) able to achieve 20 letters or more of uncorrected near visual acuity (at 14 cm) at 12 months from baseline.
- Proportion of eyes (≥75%) able to achieve improvement of 10 letters or more when comparing uncorrected near visual acuity (UCNVA) (at 14 cm) at 12 months from baseline BCNVA (at 30 cm, wearing the appropriate preoperative distance refractive correction in addition to +3.0D add).

- Proportion of eyes (≥50%) able to achieve improvement of 20 letters or more when comparing uncorrected near visual acuity (UCNVA) (at 14 cm) at 12 months from baseline BCNVA (at 30 cm, wearing the appropriate preoperative refractive distance correction addition to +3.0D add).
- Proportion of eyes (≥ 75%) able to achieve improvement of 10 letters or more when comparing best corrected near visual acuity (BCNVA) (at 14 cm) at 12 months from baseline BCNVA (at 30 cm, wearing the appropriate preoperative distance refractive correction in addition to +3.0D add).
- Proportion of eyes (≥ 50%) able to achieve improvement of 20 letters or more when comparing best corrected near visual acuity (BCNVA) (at 14 cm) at 12 months from baseline BCNVA (at 30 cm, wearing the appropriate preoperative distance refractive correction in addition to +3.0D add).

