The proportion of eyes able to achieve 20 letters or more of best corrected near visual acuity (at 14 cm) at 12 months from baseline BCNVA (at 30 cm, wearing the appropriate preoperative distance refractive correction in addition to +3.0D add).

• Change in BCNVA from baseline will be reported in lines including the following bins: loss of 15 or more letters, loss of 20 or more letters, loss of more than 5 letters, no change (within +/- 5 letters), gain of more than 5 letters, gain of 10 or more letters, gain of 15 or more letters, gain of 20 or more letters.

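### The two BCNVA secondary endpoints set no limit on the near add at 12 months in the protocol or SAP text, so the 10-letter one can be met largely by a spectacle add and a shorter reading distance

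*Protocol*

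**What the plan says.** Protocol 4.4 lists five secondary effectiveness endpoints. The last two are "Proportion of eyes (≥ 75%) able to achieve improvement of 10 letters or more when comparing best corrected near visual acuity (BCNVA) (at 14 cm") and "Proportion of eyes (≥ 50%) able to achieve improvement of 20 letters or more when comparing best corrected near visual acuity (BCNVA) (at 14 cm"). Both count letters gained "when comparing best corrected near visual acuity (BCNVA) (at 14 cm) at 12 months from baseline BCNVA (at 30 cm, wearing" a stated correction). The baseline side is fully specified: the eye is read "wearing the appropriate preoperative distance refractive correction in addition to +3.0D add". No matching statement is made for the 12-month side beyond the 14 cm distance.

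The SAP does not fill the gap. SAP 3.1.2 repeats "when comparing best corrected near visual acuity (BCNVA) (at 14 cm) at 12 months from baseline BCNVA" with the same +3.0D baseline. SAP 7.4.2 summarises, for example, "The proportion of eyes able to achieve 20 letters or more of best corrected near visual acuity (at 14 cm") at 12 months, again with no postoperative add.

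Protocol section 15 sets the BCNVA test distances (30 cm before surgery, 14 cm after, and preferred distance at both). It also lists "Add Power: Pre-Operative, 7-14 days, 30-60 days, 120-180 days, 330-420 days, Interim", with no value or upper limit.

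Inclusion criterion 10 admits "Subjects who demonstrate at least 10 letters of near visual acuity improvement with the simulation/tolerance test (using manifest refraction with +7.0D add") relative to a +3.0D add. Exclusion criterion 13 is its mirror image. Section 6.1 describes the test: Sloan near chart, +3.0D at 30 cm and at preferred distance, then +7.0D at 14 cm and at preferred distance, all before implantation.

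**The concern.** The correction is pinned on one side of the comparison and free on the other. In this protocol baseline BCNVA includes an add, and an add is determined after surgery. A site asked for best-corrected near acuity at 14 cm could therefore reasonably put up whatever add reads best there. The entry test has already shown that such an add, without the implant, gains these same eyes at least 10 letters.

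The study has no control group and no masking (SAP 6.3), so nothing else in these two endpoints separates the spectacle contribution from the implant contribution. A result above the 75% mark would be presented as effectiveness of the implant when the lens in the trial frame might account for much of it.

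**Working it through.** The plan gives no power calculation or derived sample size for these endpoints, only a cap of 10 eyes (SAP 6.2), so there is no figure to reproduce. The check sets the endpoint beside the entry test and then sizes the add-only route.

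**1. Side by side**

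| | Entry simulation, no implant (Protocol 5.1, 5.2, 6.1) | 10-letter BCNVA endpoint (Protocol 4.4) |
|---|---|---|
| Reference | +3.0D add; 30 cm and preferred distance | +3.0D add; 30 cm |
| Compared with | +7.0D add; 14 cm and preferred distance | best corrected; 14 cm; add not stated |
| Threshold | at least 10 letters | at least 10 letters |
| Needed from | every eye admitted | 75% of eyes: 0.75 × 10 = 7.5, so 8 of 10 |

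If the 30 cm and 14 cm readings decide entry, and an add near +7D is worn at 12 months, the two columns are the same contrast apart from the implant.

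**2. Optics of the add**

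- Focus at 14 cm needs 1/0.14 = 7.14 D. A +7.0D add is 0.14 D short.
- Focus at 30 cm needs 1/0.30 = 3.33 D. A +3.0D add is 0.33 D short.

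Each add is therefore close to in focus at its own test distance without any implant.

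**3. Gain from distance alone**

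- Image enlargement: 30/14 = 2.14.
- log10(2.14) = 0.331 logMAR.
- At 0.02 logMAR per letter (assumed: 5 letters per line, 0.1 logMAR per line): 0.331/0.02 = 16.5 letters.

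This holds for raw letter scores. Scoring adjusted for distance would remove it, but the entry requirement of 10 letters would remain if scoring is the same at both times.

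**4. 10-letter endpoint, add-only scenario**

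Let q be the assumed chance that an eye repeats its entry gain at 12 months. Then P(at least 8 of 10) = Σ C(10,k) q^k (1−q)^(10−k), k = 8 to 10.

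- q = 0.95: 0.99
- q = 0.90: 0.194 + 0.387 + 0.349 = 0.93
- q = 0.80: 0.68

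**5. 20-letter endpoint, add-only scenario**

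The target is 0.50 × 10 = 5 eyes. Assume add-only gains are normal with mean 16.5 letters, and keep only eyes that gain at least 10 (the entry rule). The SD is not in the documents, so a range is shown.

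| Assumed SD (letters) | P(gain ≥ 20) / P(gain ≥ 10) | Share of eligible eyes | P(at least 5 of 10) |
|---|---|---|---|
| 3 | 0.125 / 0.985 | 13% | 0.005 |
| 5 | 0.245 / 0.905 | 27% | 0.11 |
| 7.5 | 0.323 / 0.809 | 40% | 0.37 |
| 10 | 0.365 / 0.744 | 49% | 0.60 |

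The distance gain is 20 − 16.5 = 3.5 letters short of the threshold, so this endpoint is exposed but not assured.

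Steps 4 and 5 describe what an add could do in an eye like the one tested at entry. They are not forecasts for implanted eyes.

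**6. With a matched comparator**

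For 12-month acuity at 14 cm against preoperative +7.0D acuity at 14 cm, the distance term is log10(14/14)/0.02 = 0 letters. The gain required at entry also drops out of the contrast.

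**The case against.** The best defence has five parts.

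- **Appendix 3 may settle it.** Protocol section 15 sends the reader there for assessment instructions, and it was not available. This stands: the gap is established only for the protocol and SAP text. Even so, a rule that decides what the endpoint measures belongs in the endpoint definition.
- **The entry test may not be the same contrast.** Section 6.1 tests two distances per lens and does not say which pair decides the 10 letters. This stands, and the match in step 1 is conditional on it.
- **The simulation may not carry over.** At 12 months the eye has a 10-dioptre central 1.8 mm zone (Protocol section 3), and a strong add on top of it could blur that zone at 14 cm. No text says +7.0D would be used after surgery. This stands against any forecast, but not against the point that the wording permits an add.
- **The implant's effect is isolated elsewhere.** The primary endpoint and secondary endpoints 1 to 3 use uncorrected 12-month acuity. That is correct, and it limits the damage to two endpoints. Add power is recorded and listed in SAP 3.3, but SAP section 7 plans no summary of it, so reliance on an add would not show in the planned output.
- **A no-add version nearly duplicates endpoints 2 and 3.** Entry limits spherical equivalent to ±1.0D and corneal cylinder to 1.0D, so distance correction may change little. This is partly right. What the pair would still add is the removal of any residual distance error after surgery.

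The analysis is also purely descriptive, in at most 10 eyes. That lowers the stakes, but the 75% and 50% marks will still be read as success criteria.

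**Conclusion.** The point holds for the text supplied. If an add is allowed at 12 months, the 10-letter BCNVA endpoint largely repeats the entry test and cannot by itself be attributed to the implant. In the add-only scenario the chance of reaching 8 of 10 eyes is 0.68 to 0.99 for assumed repeat probabilities of 0.80 to 0.95. The 20-letter endpoint is open to the same route with much less certainty: 0.005 to 0.60 over assumed SDs of 3 to 10 letters. These sizes rest on the 30 cm and 14 cm readings deciding entry, on raw letter scoring for the 16.5 letters, and on Appendix 3 not fixing the add.

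Three stronger readings are tempting, and the documents do not support them.

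- A reader might infer that all 10 eyes would succeed with no device contribution. The entry gain was measured without the implant, and neither the deciding distances nor the postoperative add is stated.
- A reader might infer that the 20-letter mark would be met by an add. Entry requires only 10 letters. Protocol 4.5 foresees a subset gaining 20 or more in simulation but gives no share.
- A reader might infer that an explanted eye could count as a responder. Acuity and add are recorded after removal, but on separate forms timed from removal, and the SAP does not say that those values enter this endpoint.

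This should be corrected. It does not touch the primary endpoint.

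**What to change.** - In Protocol 4.4 (fourth and fifth endpoints), SAP 3.1.2 and SAP 7.4.2, define the 12-month value as distance-corrected near acuity at 14 cm with no near add. Give it its own name, so that it is not confused with BCNVA.
- Keep BCNVA with any add for the safety endpoint (Protocol 4.1, SAP 7.5.2) and for SAP 7.5.7.2, and report the add power used beside it.
- Removing the add still leaves 30 cm on one side and 14 cm on the other. So also report the 12-month 14 cm value against the preoperative +7.0D simulation acuity at 14 cm, which is already collected. Distance and magnification are then matched.
- If Appendix 3 already sets the postoperative add, carry that rule into the endpoint text and bring the two into line.

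The cost is wording in two documents, a case report form line stating that no add was worn, and one short extra acuity reading. The sample size does not change. The reported responder rate may be lower.
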